3. BACKGROUND

Trainers are more frequently employing high-fidelity medical simulation to allow learners to acquire complex skills at minimal risk to real patients.¹ The presence of critical observers during such training invokes a stress response and emotional reactions in participants. Invoking emotional responses, both positive and negative, appears to enhance the participant's memory of the event and can ameliorate learning.² Some educational researchers take advantage of such responses to overcome the challenges presented by workload, rising expectations, and resource limitations to create a memorable simulation learning event.

The utility of stress for enhancing learning is controversial and its use may be a net negative.^{2,3} Stress is closely associated with anxiety and is generally considered a negative occurrence. Cognitive appraisal theory considers the perception of whether the resources available to a person facing a stressful incident are adequate; if they are, then the situation is viewed as a challenge whereas inadequate resources cause the situation to be seen as a threat. Situations perceived as a threat invoke anxiety in the subject and activate biological pathways, specifically in the sympathetic nervous system and the hypothalamic-pituitary-adrenal axis.^{4,5} Endocrine activity causes the subject to be more attentive and perceptive and to develop stronger memories of the threatening events.⁶⁻⁹ There appears to be a direct correlation between the cortisol levels in an individual during an event and the degree of retention of the memory of that event, though heightened cortisol may negatively affect the recall of older memories during the event.⁶ Despite the promising evidence in favour of heightening cortisol during learning, educators almost must consider the consequences of inflicting negative emotions and stress onto participants. The positive effects of cortisol on memory decay as cortisol concentrations increase, ultimately causing impairment of learning and performance at very high levels.⁸ On the other hand, situations appraised as a challenge are not accompanied by cortisol release and may result in less retention.¹⁰

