4.2 Secondary Objectives

Our secondary objectives are:

- (i) To assess if unexpected death of a simulated patient is associated with an impaired retention of technical resuscitation skills.
- (ii) To examine if unexpected death of a simulated patient is associated with future higher stress levels and stronger emotions during simulated crisis.
- (iii) To investigate the relationship between stress levels as well as emotions and future performance in crisis.

We furthermore hypothesize, that simulated death will lead to higher stress levels as well as more negative emotions and will thereby impact the ability to retain critical skills.

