7.2 Sample size considerations

A priori sample size calculation was performed on the basis of an estimated Cohen's *d* effect size of 0.8, which is considered large and acceptable for a teaching intervention.³³ We aim at a two-tailed level of significance of $p < 0.05$ and a power of 0.8. Using the recommended sample size estimation approach for ANCOVA³⁴ with an estimated r^2 of 0.12, derived by a previous, not now published trial ([name] et al, Learning crisis resource management: Practice versus observing, CAS 2013 Abstract 1653689, accessible at <http://www.cas.ca/English/AM-Abstracts-2013>), a number of 46 participants would be needed. In order to account for an estimated attrition rate of 20% we need to recruit 56 participants. G*Power for MAC (version 3.12, Düsseldorf, Germany) was used for sample size calculations.

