7.3 Statistical analysis

As it has been suggested as best practice for stratified randomized controlled trials, ANCOVA will be used to analyze the outcome parameters using the level of training (PGY1-3 vs PGY 4-5 and fellows) and specialities (acute care specialities vs. non-acute care specialities) as covariates.³⁵ Group assignment (unexpected death, alive) will be used as the independent variable. Demographic data will be analyzed using an unpaired Student's *t*-test or chi-square test, where appropriate.

Curved/linear regression analysis will be performed to assess the correlations between each outcome and stress as well as emotions. As it is common practice, results of Likert-like scales will be treated as interval-measures and thereby analyzed by using parametric tests.^{36,37}

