Impact of Unexpected Death in Simulation: Skill Retention, Stress and Emotions

Data Analysis Plan

Primary Outcome: Difference in retention of non-technical crisis resource management (CRM) skills using Ottawa Global Rating Scale (OGRS)

ANCOVA:

- Dependent variable: OGRS score (total score)
- Independent variable: Death vs. survival
- Covariates: Junior vs. senior; Acute vs. non-acute

Secondary Outcome 1: Technical CRM skills (according to checklist)

- Same Videos to be provided for primary outcome will be scored using the “Task-specific checklist” (derived from American Heart Association’s Megacode Checklist) and given a score out of 18

ANCOVA:

- Dependent variable: Task-specific checklist score (total score)
- Independent variable: Death vs. survival
- Covariates: Junior vs. senior; Acute vs. non-acute

Secondary Outcome 2: Stress

Measure 1: Salivary cortisol

Five time points (minutes passed since baseline):

1. Baseline (0 minutes) during the accommodation period at the beginning of the day
2. Before scenario (10 minutes)
3. Immediately after scenario (30 minutes)
4. 30 minutes after start of scenario (45 minutes)
5. After debrief (50 minutes)

ANCOVA:

- Dependent variable: Change in cortisol concentration (versus baseline) at a given time point (for each time point)
- Independent variable: Death vs. survival
- Covariates: Junior vs. senior; Acute vs. non-acute

Regression:

- Linear regression to determine the effects of covariates (Junior vs. senior; Acute vs. non-acute) on change in cortisol concentration over time
 - Separated into “death” and “survival” groups
 - Change in cortisol concentration will be established using the baseline reading of each participant on each day of the study (time point 1).
- Unpaired t-tests will be used to compare change in cortisol levels between the “death” group and the “survival” group at each time point.

Measure 2: State-Trait Anxiety Inventory (STAI)

- Analysis will be carried out in the same way as the cortisol measures with the STAI score taking the place of the change in cortisol concentration

Measure 3: Cognitive appraisal

- Mean cognitive appraisal ratios for each group (“death” and “survival”) at each time point will be calculated and subjected to a one-sample t-test to determine whether they are significantly different from 1.
- Unpaired t-tests will be used to compare the mean ratios of the “death” and “survival” groups at each time point.

Secondary Outcome 3: Valence of emotions

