Five-point Likert scale

Repeated measures ANCOVA:

- Dependent variable: Score for each emotion
- Independent variable: Death vs. survival
- Covariates: Junior vs. senior; Acute vs. non-acute
- Time points: Initial and retention

For all Outcomes:

Relationships between all outcomes (determined by ANCOVA or by Pearson’s correlation) will be presented in a matrix table.

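### The SAP does not carry forward the curved/linear regression of performance on stress planned in protocol 7.3; its Pearson matrix cannot show the rise-then-fall shape described for cortisol

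*SAP*

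**What the plan says.** Protocol 4.2 lists as secondary objective (iii): "To investigate the relationship between stress levels as well as emotions and future performance in crisis". Protocol 7.3 supplies the method: "Curved/linear regression analysis will be performed to assess the correlations between each outcome and stress as well as emotions". It does not say what form the curve takes.

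Protocol section 3 gives a reason to expect a curve for cortisol: "The positive effects of cortisol on memory decay as cortisol concentrations increase, ultimately causing impairment of learning and performance at very high levels". The same section also reports a direct correlation between cortisol during an event and later memory of it.

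The SAP covers relations between outcomes in one sentence under its closing heading, For all Outcomes: "Relationships between all outcomes (determined by ANCOVA or by" Pearson's correlation) will be presented in a matrix table. It does not say which test occasion's stress is paired with which occasion's performance, or whether the two arms are combined, separated or adjusted for.

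Elsewhere, each ANCOVA in the SAP has death versus survival as the independent variable and the two strata as covariates. The only regression is under Measure 1 of Secondary Outcome 2: "Linear regression to determine the effects of covariates" (training level and specialty) on change in cortisol, run separately by group. STAI is to be handled in the same way.

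**The concern.** An analyst working from the SAP alone would have only Pearson's r for objective (iii). The specified ANCOVAs contain no stress or emotion predictor, and the one regression explains cortisol by training level and specialty, not performance by stress.

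Pearson's r measures the straight-line part of a relation. If moderate cortisol helps retention and very high cortisol harms it, r can be near zero while the relation is substantial. The trial could then report no relation between stress and retention. If most participants lie on the rising side, r may be significant, but it would describe a steady rise and leave out the later fall.

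There is a second, conditional risk. The protocol hypothesises that death raises stress and impairs retention. If the correlations are computed across both arms without adjustment, the two arm effects alone would produce a negative stress-performance correlation.

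**Working it through.** **Sample size.** Protocol 7.2 states: "We aim at a two-tailed level of significance of" 0.05 "and a power of 0.8", with Cohen's d = 0.8 and r² = 0.12. A two-sample t-test on these inputs needs 26 per arm, 52 in total. Then 52 × (1 − 0.12) = 45.76, rounded up to 46, which is the protocol's figure. 46 × 1.2 = 55.2, rounded up to 56, is the recruitment target. The documents give no power figure for the stress-performance analysis, so n = 46 is used below.

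**Does Pearson's r see an inverted U?** Let x be stress, standard normal, and let performance be −(x − c)² plus normal noise, where c is the peak in SD above mean stress and R² is the share of variance the curve explains. The curve has variance 2 + 4c² and covariance 2c with x, so

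r = √R² × 2c / √(2 + 4c²).

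- c = 0: r = 0, whatever R² is.
- c = 1, R² = 0.20: r = 0.447 × 2/√6 = 0.365.
- c = 2, R² = 0.20: r = 0.447 × 4/√18 = 0.42.

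**Rejection rates**, n = 46, two-sided 0.05, 20,000 simulated trials per setting (Monte Carlo standard error at most √(0.25/20,000) = 0.35 percentage points). The normal distribution, c and R² are assumptions. The three values in each cell are for R² = 0.12 / 0.20 / 0.30.

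| Peak above mean | Pearson (%) | Linear + quadratic, 2-df test (%) | Quadratic term alone (%) |
|---|---|---|---|
| 0 SD | 9.6 / 13.0 / 16.8 | 52.2 / 75.1 / 90.1 | 58.5 / 79.6 / 92.4 |
| 0.5 SD | 29.2 / 43.4 / 57.1 | 53.2 / 75.5 / 90.7 | 44.6 / 65.6 / 82.8 |
| 1 SD | 49.5 / 69.9 / 85.8 | 54.2 / 77.6 / 92.4 | 25.8 / 41.9 / 60.2 |
| 2 SD | 60.7 / 83.6 / 95.8 | 54.7 / 80.1 / 94.6 | 11.6 / 17.7 / 26.9 |

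The 2-df test keeps nearly the same power wherever the peak lies, while Pearson depends heavily on its position. Attrition of 20% from 56 leaves 44.8. At n = 45 and R² = 0.20 with a central peak, the rates are 12.8% and 73.9%, so little changes.

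**Skewed stress.** With a standardised lognormal stress score (log-SD 0.5) and R² = 0.20, Pearson rejects in 35.9%, 20.6%, 28.3% and 71.0% for peaks at 0, 0.5, 1 and 2 SD. The 2-df test rejects in 47.6%, 45.5%, 57.7% and 79.3%. The direction holds, with less power for the 2-df test.

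**If the arms are pooled.** Suppose death shifts stress by d₁ = +0.8 SD and performance by d₂ = −0.8 SD, with no relation within either arm and 1:1 allocation. Then

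r = 0.25·d₁·d₂ / √[(1 + 0.25·d₁²)(1 + 0.25·d₂²)] = −0.16/1.16 = −0.138.

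With 23 per arm this reaches p < 0.05 in about 15% of trials instead of 5%. Adjusting for group removes the excess. The 0.8 is borrowed from the protocol's design effect for performance; an equal shift in stress is an assumption.

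**The case against.** Several points on the other side stand.

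- A reader might infer that the SAP replaced the protocol's regression. The documents do not support that. The SAP never withdraws section 7.3, and neither document says which governs. The SAP is equally silent on the demographic comparisons in 7.3 and the qualitative analysis in 7.4. What can be said is that it does not carry the regression forward. The protocol's wording also allows a purely linear fit.
- A reader might infer that the SAP pools the arms. It does not say so, and its cortisol regression is split by group. The point is unspecified, and the artefact computed above is modest.
- A reader might infer that Pearson is blind to the relation. That is true only for a peak at mean stress. The Background places impairment at very high cortisol and also mentions a direct correlation, which fits a peak well above the mean at least as well. In that case Pearson detects the association about as often as the 2-df test, and the quadratic term alone would usually be missed.
- The curve is stated for cortisol only. Nothing comparable is stated for STAI, appraisal or emotion, so quadratic terms for those measures do not follow from the documents.
- The R² values are assumptions. At 0.12, the only variance figure in the protocol (given there for the ANCOVA), the 2-df test reaches only about 52% to 55%. These rates are also for a model without the adjustment proposed below.
- The objective is secondary, and protocol 8.2 describes all parts of the study as serving to generate hypotheses.

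None of this removes the mismatch. An analyst following the SAP would still not fit the regression the protocol promises, and Pearson would still not show a turning point.

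**Conclusion.** The point holds as an omission in the SAP that affects a secondary, exploratory objective. The primary comparison of the arms is untouched.

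The loss depends on where the cortisol peak lies, which the documents do not give. It is large if the peak is near average stress, small at 1 SD above the mean, and absent or slightly reversed at 2 SD under normally distributed stress. In every case the Pearson matrix leaves the shape unexamined, although the protocol's own theory turns on it. The confounding by arm arises only if the correlations are pooled without adjustment, which the SAP leaves open.

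**What to change.** Write the protocol 7.3 regression into the SAP for objective (iii):

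- Regress the retention OGRS total and the retention checklist score on one prespecified initial-test cortisol measure, with linear and quadratic terms tested jointly on 2 degrees of freedom.
- Regress the same two scores on initial-test STAI, cognitive appraisal and emotion, with at least a linear term each.
- Adjust every model for group, both strata and the initial-test score on the same scale.
- Label these models exploratory and the Pearson matrix descriptive, and state whether the matrix is computed by arm or overall.
- State which document governs where the protocol and SAP differ.

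The cost is SAP wording and analysis time; all the data are already planned. The quadratic term takes one extra degree of freedom per cortisol model. The adjusted cortisol model has 7 coefficients (intercept, two for cortisol, group, two strata, initial score), leaving 46 − 7 = 39 residual degrees of freedom. Two outcomes by four kinds of measure is at least eight models, and more if emotions are scored singly, so the results should be read as a set and not as separate tests. Power for the quadratic term itself stays limited if the peak is far above the mean.
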